The changes in the mean fatigue scores were -0.58, -5.16, and -2.66 for the control, EXER, and COMB groups respectively, from pre-test to immediately post-intervention in the pilot study. The Cohen's d effect sizes for the EXER and COMB groups were 0.51 and 0.23, respectively; whereas the overall effect size was 0.21. As no similar cluster-RCT has been reported in the literature and the cause of general fatigue is heterogeneous, we assumed that an intra-correlation coefficient would be low (0.01) within each cluster (43). Based on an effect size of 0.21 in the pilot study, and four clusters (community centres) per group with an intraclass correlation of 0.01, a significance level (α) of 0.05, and a power ($1-\beta$) of 0.8 for a two-sided test, the sample size was calculated to be 76 participants per group according to NCSS PASS 14. For a long-term follow-up of 12 months, 285 participants (95 per group) will be recruited after considering an attrition rate of 20%. Using computer-generated random numbers, a biostatistician not affiliated with this study will randomize the centres into either: control, EXER, or COMB. The randomization will be stratified based on the size of the centres. Small-medium centres will be defined as those with < 800 ($n=9$) clients, whereas those with > 800 clients will be defined as large ($n=3$). The number of participants recruited in each centre will be in proportion to the size of the centre (i.e., the total number of clients). We estimate that about 25-50% (4, 16, 44) of the 8,710 members of these centres will be eligible to participate. To avoid selection biases, the allocation to the study groups will be concealed from the researchers until the recruitment of the sample and measurement of the baseline have been completed (please refer to the item 13 in this application for details of the collaborators).

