Interventions: (*Appendix II:* Overview of the combined intervention) A 16-week programme with a combination of exercise and the BCE programme (plus two booster BCE sessions will be held at 2 and 6 months after the programme) will be arranged for the COMB group. Another 16-week programme with a combination of exercise and health talks will be arranged for the EXER group, whereas participants in the control group will attend only the health talks with no other intervention. Two added health talks will be arranged at 2 and 6 months after the programme for the EXER and the control groups. To control the group and social interaction effects of the BCE programme for the COMB group, the number and timing of the health talks for the other two groups will be similar to those in the BCE sessions. All face-to-face sessions will have < 10 participants to maintain good interactions between the participants and the exercise instructor / BCE facilitator/ health talk speakers.

The behavioural change enhancement (BCE) programme in the COMB group (Appendix III: BCE programme protocol) aimed at motivating the participants to develop the intention to actively manage their fatigue; and to encourage them to gradually exceed the perceived limits of their energy and to recondition their bodies by participating in exercise according to their individual exercise regimens. The BCE programme was designed based on the HAPA model and was piloted by the PI

(14). It consists of three phases with six face-to face one-hour sessions plus two booster BCE sessions at 2 and 6 months. The first three weekly sessions will be arranged during the ‘goal initiation’ and ‘planning’ phases. The remaining three sessions and two booster sessions will be offered once per month in weeks 4, 8, and 12 during the programme; and at 2 and 6 months after the programme during the ‘action execution’ phase.

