Exercise intervention in the EXER and the COMB groups: A weekly 45-60 minute centre-based exercise programme, which designed according to the American Heart Association’s recommendations on exercise for older people (48), will be arranged from weeks 4-16 during the execution phase. This programme will consist of balance training, such as sideways walking (15-20 minutes); resistance exercises, such as using resistance bands to improve muscle strength in both the upper and lower limbs (10-20 minutes); aerobics training, such as walking (10 minutes) and with 10 minutes of warm-up and cool-down exercises at the beginning and at the end. All participants will receive circuit training with set exercises, but the dosage of different components will be tailor-made for each participant based on his/her physical conditions. The first assessment will be in week 4 (i.e., the first week of the exercise programme), and subsequent monthly assessments will be held in weeks 8 and 12 by a physiotherapist. The dosage of exercises will gradually increase by increasing the number of repetitions, the duration of the exercises, and also by using progressively heavier wrist and ankle weights maintained at approximately 12-14 on the Borg Rate of Perceived Exertion Scale(28, 49), based on the participants’ progress. The dosage of exercise recommended to each participant by the physiotherapist will be recorded. Demonstrations and return demonstrations will be performed during the training to ensure that the participants are able to do the exercises properly. A compact disc and a pamphlet describing the different types of exercises used in this programme will be disseminated to all participants to encourage them to continually practice their exercises at home for approximately 30 minutes at least 3 times per week. Although this set of exercises was used in the pilot study with no reports of adverse effects, safety guidelines on exercise for older people will be discussed with all of the participants.

The Control Condition: Participants in the control and EXER groups will attend centre-based health talks on the management of different health issues with the exception of fatigue. Another RA, who will not be involved in other procedures of this study, will run the health talks.

Instruments and Measures

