SPSS version 23.0 will be used to analyse the data. An intention-to-treat analysis will be adopted. Descriptive statistics will be generated for the demographic data. Normality assumptions for the variables will be checked. The baseline characteristics of the participants in the three groups will be compared using ANOVA for the continuous variables, a chi-square test for the categorical variables, and the Kruskal-Wallis test for the ordinal variables. Mixed-effects modelling will be used to measure changes in the outcome assessments across the mid-term programme (at week 8) and the three post-tests (1 week, 6 months, and 12 months after the intervention) among the three groups, followed by the Helmert contrasts test (if any results are found to be significant)(60). Another mixed-effects modelling approach will be used to measure the participants' attendance rate in the weekly exercise sessions and their adherence to the home exercise during the programme and the follow-up period between the EXER and the COMB groups. Any pre-test outcome scores, demographic information, data on health conditions, comorbidity index, health service utilization, dosages of exercise recommended by the physiotherapist, and participation in other exercise programmes during the study period, indicating significant differences between groups, will be treated as co-variates as needed. Multiple imputations will be adopted to manage missing data. A p-value of < 0.05 will be considered statistically significant. Content analysis will be used to analyse the interview data⁶¹. All audio-taped interviews will be transcribed into Chinese by the RA and the transcriptions will be checked for accuracy by the PI using QSR NVivo 11. The revised transcripts will be coded independently by two (Chinese-speaking) Co-Is. The research team will then discuss the identified codes and come to an agreement on them, grouping them into main (sub)categories with the support of verbatim data. The (sub)categories will then be condensed and/or re-organized when deemed necessary. The research team will examine them for consistency, reach a consensus about their meaning and structure, and devise a list of finalized categories. A set of (sub)categories with supporting verbatim data will finally be generated to identify the major strengths and limitations of the combined intervention to come up with improvements for its future use.

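### The SAP lets variables that arise after randomisation become covariates when arms differ, and does not keep them out of the three-arm outcome models

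*SAP*

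**What the plan says.** The SAP states: "An intention-to-treat analysis will be adopted". It describes two models. For the outcomes, "Mixed-effects modelling will be used to measure changes in the outcome assessments across the mid-term programme" and at the three later assessments, in all three groups. A second mixed model compares exercise attendance and home-exercise adherence between EXER and COMB only.

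The covariate sentence comes after both models. It opens "Any pre-test outcome scores, demographic information, data on health conditions, comorbidity index, health service utilization" and closes "dosages of exercise recommended by the physiotherapist, and participation in other exercise programmes during the study period, indicating significant differences between groups". Variables that meet this condition become covariates where that is thought necessary. The sentence does not say which model it governs.

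The Protocol adds four facts:

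- **Procedures:** centres are randomised after the baseline assessment.
- **Exercise intervention in the EXER and the COMB groups:** "The dosage of exercise recommended to each participant by the physiotherapist will be recorded". The first physiotherapist assessment is in week 4, and "subsequent monthly assessments will be held in weeks 8 and 12 by a physiotherapist".
- **Interventions:** "participants in the control group will attend only the health talks with no other intervention".
- **Instruments and Measures, socio-demographic data:** service use is collected at every assessment, for the year before the study and for the study itself. It may be a covariate if required. The two periods are not separated.

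**The concern.** Adjusting for variables fixed at baseline is compatible with intention to treat. Adjusting for a variable that allocation may have altered is different, because part of the effect of assignment can be removed, or a spurious difference added. Recommended dose is part of the intervention and is not defined for controls. Other exercise and on-study service use are defined in every arm. The documents do not say that allocation changes them, but it could.

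The entry rule makes this worse. A significant difference between arms is the sole stated test, so the rule tends to pick the variables that allocation has moved. Which variables enter, and in what model form, is left to a decision made after the data are seen. At stake is whether the reported arm differences in fatigue and the secondary outcomes can be read as effects of assignment.

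**Working it through.** The documents give no figure for this point, so there is none to reproduce. The check has a textual part and an arithmetic part.

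**1. Timing of each listed item**

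| Item | When fixed | Arms where defined |
|---|---|---|
| Pre-test scores, demographics | Before randomisation | All |
| Service use, year before baseline | Before randomisation | All |
| Service use during the study | After | All |
| Other exercise during the study | After | All |
| Recommended dose | After (weeks 4, 8, 12) | EXER, COMB |

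**2. Inputs**

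- From the Protocol's sample size section: 76 per arm after attrition, 95 recruited; level 0.05 (SAP).
- From the pilot (same section): "The changes in the mean fatigue scores were -0.58, -5.16, and -2.66 for the control, EXER, and COMB groups respectively". Hence EXER v control = -5.16 + 0.58 = -4.58; COMB v control = -2.66 + 0.58 = -2.08; EXER v COMB = -5.16 + 2.66 = -2.50.
- SD: 4.58/0.51 = 8.98, taken as 9.
- Assumed, because the documents are silent: slopes, uptake rates, service-use gaps, and a between-visit correlation of 0.5. Clustering is ignored.

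**3. Smallest gap that passes the screen (76 per arm)**

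- Two arms (dose): t(150) × √(2/76) = 1.976 × 0.162 = 0.32 SD. At 95 per arm it is 0.29 SD.
- Three arms, continuous: √(2F/(76 × 2/3)) with F(2,225) = 3.04 gives 0.35 SD between the extreme arms. This minimum applies when the third arm equals one of the extremes; with the third arm midway it is √(4F/76) = 0.40 SD.
- Three arms, yes/no variable with 20% average uptake: √(5.991 × 0.2 × 0.8/(76 × 2/3)) = 0.138, about 14 percentage points. With the third arm midway it is about 16.

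**4. Shift if the T0 score is a covariate or change scores are analysed**

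By the least-squares identity, adjusted difference = unadjusted difference - (gap between arms × within-arm slope). The gaps below are population gaps, so the results are expected values.

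- *Dose, EXER v COMB, at the threshold:* 0.32 × 1, 2 or 3 points per SD = 0.32, 0.64 or 0.96 points, which is 13%, 26% or 38% of 2.50. At a 0.4 SD gap and 2 points per SD the shift is 0.8, so -2.50 becomes -1.7, or -3.3 with the gap reversed.
- *Other exercise, 3 points lower fatigue if taken up, uptake 15/25/30% (control/EXER/COMB):* shifts 0.10 × 3 = 0.30 and 0.15 × 3 = 0.45. EXER and COMB v control go from -4.58 and -2.08 to -4.28 and -1.63. With uptake 30/25/15% they go to -4.73 and -2.53. The screen passes in about 51% of trials in either direction at 76 per arm (about 61% at 95).
- *On-study service use, 2 points per SD, EXER 0.3 and COMB 0.4 SD below control:* shifts 0.6 and 0.8, giving -3.98 and -1.28. The screen passes in about 62% of trials.

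For scale, the standard error of an arm difference adjusted for T0 is 9 × √(1 - 0.5²) × √(2/76) = 1.26 points. The other-exercise shifts of 0.30 and 0.45 are 0.24 and 0.36 of that; the service-use shifts of 0.6 and 0.8 are about 0.5 and 0.6.

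**5. Dependence on model form**

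If T0 is one of the repeated outcomes and the variable enters as a person-level main effect, it adds the same amount at every visit and cancels from the group-by-time contrasts. Simulation with uptake 15/25/30% confirms this: -4.6 and -2.0 with or without the covariate. With T0 as a covariate and four post-baseline visits, the same data give -4.3 and -1.6 after adjustment. The SAP speaks of modelling changes and also lists pre-test scores as covariates, so it does not settle which form applies.

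**The case against.** The strongest reply is that the covariate sentence follows the adherence model directly and may have been written for it. Dose is recorded only in the exercise arms, and Appendix V limits adherence to the same arms. For dose this reading is plausible, and entering dose in a three-arm model would need a control code that no document gives; the conclusion does not rest on that case. The reading does not cover the whole list. Pre-test outcome scores fit the outcome models, other exercise and service use exist in all arms, and the Protocol's clause on service use has no link to adherence. Even between EXER and COMB, dose is first set after the three opening weekly behavioural sessions, so assignment could affect it.

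Second, the wording is permissive. Harm requires that allocation changes the variable, the gap is significant, the team chooses to adjust, the variable enters an outcome model, and the model form transmits the shift. That is true and limits the certainty of harm. It also describes a choice made with the data in view.

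Third, the slopes and gaps are assumed, and the other-exercise and service-use shifts are below one standard error. Both points stand. The shifts are nevertheless biases, which a larger sample does not remove, and a larger sample makes the screen easier to pass. One ordinary model form shows no shift, but only for a person-level main effect. Service use is collected at each visit and could enter as time-varying, a case not examined here.

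**Conclusion.** The concern holds. The SAP's rule can bring post-randomisation variables into the three-arm outcome models, selected because arms differ, under a declared intention-to-treat analysis. That follows from the text and does not depend on the illustrations.

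The size is uncertain. In the illustrations, arm differences move by about 0.15 to 0.96 points, in either direction, against pilot differences of 2.08 to 4.58 points. These figures rest on assumed slopes and gaps and on a form with the T0 score as covariate or with change scores. There is no shift if the variable is unrelated to allocation, or if T0 is a repeated outcome and the variable enters as a person-level main effect. This should be fixed before the data are analysed. Confidence that it would matter in practice is medium.

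**What to change.** In the SAP:

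- State that the three-arm outcome models adjust only for prespecified variables measured at T0. Service use in the 12 months before baseline may remain a candidate. Remove the significance screen as the route of entry to these models.
- Report recommended dose, other exercise and on-study service use by arm descriptively, or in an analysis labelled exploratory, with dose confined to EXER and COMB.
- State separately which covariates, if any, belong to the EXER v COMB adherence model.

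In the Protocol's socio-demographic data paragraph, limit the use of service use as a covariate in the outcome models to the pre-baseline period.

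The cost is SAP wording and one Protocol clause. No extra data are needed and nothing changes for participants. If the sponsor always meant the later variables for the adherence model only, the same edit records that.

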Participants will be assessed on a variety of outcomes (described below) at week 8 (T1 at mid-term programme), 1 week (T2 immediate effect), 6 and 12 months after the programme (T3 and T4), which will be compared with the baseline assessment (T0). All assessments will be carried out by a part-time RA, regarded as an independent assessor, who will be blinded to the group assignments.

Socio-demographic data: The following data will be collected: 1) age, gender, marital status,

exercise habits, living conditions, and level of education, 2) the participants' health-related information, including cognitive status and medications. Additionally, their levels of comorbidity will be assessed using the Chinese version of the Charlson comorbidity index (C-CCI). The C-CCI score is the sum of the comorbidity and age scores, in which scores of 0, 1-2, 3-4, and > 5 represent the comorbidity level as none, low, medium, and high, respectively⁵⁰. The health services utilization of the parents in the past 12 months and during the study period, such as the number, duration, and causes of hospital admissions and scheduled/non-scheduled clinical visits, will be collected during each measurement time point and will be treated as a co-variate if needed.

Primary outcome measurement: Fatigue will be assessed using the 20-item Chinese Multidimensional Fatigue Inventory (CMFI-20)⁽⁵¹⁾. This scale was validated among 385 local cancer patients. A factor analysis revealed that it contains three factors (namely, physical, mental, and spiritual) with a factor loading ranging from 0.52 to 0.75. The Cronbach's α was between 0.7 and 0.8 for three domains and the total of the CMFI-20 score. It supports the view that the CMFI-20 is a reliable and valid instrument.

Secondary outcome measurements

Physical Endurance will be evaluated using different physical tests. First, the participants' lower-limb and upper-limb strength will be assessed using a 30-second chair stand test⁽⁵²⁾ and a handheld Jamar Hydraulic Hand Dynamometer⁽⁵³⁾, respectively. Their mobility and overall physical endurance will be assessed through the TUG test and by their gait speed (6-m walk).

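### An outcome's baseline score is adjusted for only if a significance test that ignores centres finds the arms different; fixed adjustment for T0 would be more precise at almost no cost

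*SAP*

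**What the plan says.** The SAP sets out a baseline comparison: "The baseline characteristics of the participants in the three groups will be compared using ANOVA for the continuous variables", with chi-square and Kruskal-Wallis tests for the other variable types. No centre term is mentioned. It then lists candidate covariates, beginning "Any pre-test outcome scores, demographic information, data on health conditions, comorbidity index, health service utilization". Those "indicating significant differences between groups, will be treated as co-variates as needed". No other sentence in either document makes an outcome's T0 score a fixed covariate.

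On the outcome model, the SAP says: "Mixed-effects modelling will be used to measure changes in the outcome assessments across the mid-term programme (at week 8) and the three post-tests". T0 is not among the time points listed, yet the word used is changes. The Protocol (Instruments and Measures) says that follow-up assessments are compared with T0, without saying how. Random effects are not stated.

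The design is cluster-randomised. The Protocol's sample size section assumes "four clusters (community centres) per group with an intraclass correlation of 0.01", and its Procedures section confirms that the twelve centres are what is allocated.

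The covariate list also contains variables measured after randomisation. This point is about the baseline ones only.

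**The concern.** The T0 value of an outcome is usually among its strongest predictors. Adjusting for it reduces variance whether or not the arms happen to differ at T0, so a significance test is the wrong gate. There are three consequences.

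- **Precision.** In most trials the test will be non-significant and T0 adjustment will be left out.
- **Imbalance below the threshold.** Let G be the observed baseline gap between two arms. A change score subtracts all of G when only rG should be removed, so it over-corrects by (1 − r)G. A post-score model removes none of it, so rG stays in the estimate. Adjustment for T0 removes the right amount on average.
- **A covariate set chosen by chance.** Participant-level tests in a cluster design reject too often, and the words *as needed* leave a further choice open after the data are seen.

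The primary fatigue comparison is affected, along with every secondary outcome that has a T0 score.

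**Working it through.** **Inputs from the Protocol's sample size section.** Four centres per arm, 76 evaluable per arm (76/4 = 19 per centre), 95 recruited per arm (76/0.8 = 95, which reproduces the stated figure), ICC 0.01, two-sided α 0.05, and pilot effect sizes of 0.51 (EXER) and 0.23 (COMB). The 76 is taken as given here. A three-group ANOVA with f = 0.21 gives 74 per group with clustering ignored and 87 with a design effect of 1.18, but that is a separate matter.

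**Assumed.** The correlation r is not in the documents, so it is varied from 0.3 to 0.8, equal within and between centres. Other assumptions are d = 0.51 on the score SD, EXER v control, one follow-up, and a centre-level test with 12 − 3 = 9 df.

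**Step 1: relative variance of the arm difference.** Post-score 1; change score 2(1 − r); T0-adjusted 1 − r². Adjusted over change is (1 + r)/2, and adjusted over post is 1 − r². Both are below 1 for any r between 0 and 1.

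**Step 2: power.** The design effect is 1 + 18 × 0.01 = 1.18. The non-centrality is 0.51 × √(76 / (2 × 1.18 × V)), where V is the relative variance, and the critical t on 9 df is 2.262. At r = 0.5, change and post-score both have V = 1, giving 2.89 and 73% power; adjusted has V = 0.75, giving 3.34 and 84%.

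These figures take T0 as never adjusted for. The SAP rule adjusts in the few trials where the baseline test is significant, so its loss was simulated. The last two columns give the loss in percentage points under the rule against always adjusting.

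| r | Change, never adjusted (%) | Post, never adjusted (%) | Always adjusted (%) | Loss under rule, change | Loss under rule, post |
|---|---|---|---|---|---|
| 0.3 | 59 | 73 | 77 | 16 | 3 |
| 0.4 | 65 | 73 | 80 | 13 | 6 |
| 0.5 | 73 | 73 | 84 | 10 | 10 |
| 0.6 | 82 | 73 | 89 | 6 | 14 |
| 0.7 | 91 | 73 | 95 | 3 | 19 |
| 0.8 | 98 | 73 | 99 | 1 | 23 |

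A repeat simulation of 20,000 trials per r agreed within about one point. With no true effect, the rule rejected in about 5% of trials or slightly fewer.

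**Step 3: how often the baseline test flags a chance difference.** The F statistic is inflated by the design effect. At 19 per centre this is 1.18 and the flag rate is 7.9%. At 95/4 = 23.75 per centre it is 1 + 22.75 × 0.01 = 1.2275 and the rate is 8.7%. With ICC 0.05 the rates are about 20% and 24%. At ICC 0.01 the rule therefore leaves T0 out in about 92% of trials.

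**Step 4: the largest gap that passes as non-significant.** With 95 per arm the critical F(2,282) is 3.03. If the third arm lies midway, F = 95G²/4, so G = √(4 × 3.03/95) = 0.36 SD. If the third arm coincides with one outer arm, F = 95G²/3, so G = √(3 × 3.03/95) = 0.31 SD. At r = 0.5, a gap of 0.36 SD puts 0.5 × 0.36 = 0.18 SD into the estimate, with opposite sign for change scores and the same sign for post-scores. The pilot COMB effect was 0.23.

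**The case against.** **T0's role is unspecified.** This is the strongest objection, and it stands. A reader might infer that T0 enters the model only through the significance gate and that a sub-threshold gap is left uncorrected. The documents do not support that. If change is analysed, T0 is already used and the gap is over-corrected. If T0 is a response with free baseline means, the contrast with complete data is again the change-score contrast. Only a model with T0 as a response and baseline means held equal would avoid the loss, and neither document specifies one.

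**No single figure bounds the loss.** A reader might quote 13 points as the maximum. It is only the change-score value at r = 0.4; the figure depends on r and on the reading.

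**Effect scale.** The effect sizes appear beside mean changes, and they imply an SD near 9 (4.58/0.51 and 2.08/0.23). That may be the SD of change. If so, unadjusted change-score power is about 73% at every r, and the loss against always adjusting is about 14 to 7 points over r = 0.4 to 0.7. The trial is also sized on 0.21, and the planned model uses four visits and three groups, so the table illustrates the loss and does not predict it.

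**False positives.** A reader might infer that the rule inflates type I error. It does not, and averaged over randomisations the estimate is not biased.

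**Many variables tested.** A count of chance flags across all baseline variables would need them to be independent. They are not: gait speed, grip strength and PASE-C are components of the frailty index.

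**Conclusion.** The point holds. Covariate status for T0 depends on a baseline significance test that names no centre term, and then on a further judgement of need. On a change-score or post-score reading this is less precise than fixed adjustment at every r examined. Under the stated assumptions the loss at r = 0.5 is about 10 points of power on either reading. It is about 1 to 16 points for change scores and 3 to 23 for post-scores over r = 0.3 to 0.8. A gap of 0.31 to 0.36 SD between the outer arms can escape the test, and the test flags chance differences in about 8 to 9% of trials at ICC 0.01.

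That the rule exists and that fixed adjustment is better are well supported. The exact size is not, because r and the model's use of T0 are missing from the documents. The harm is lost precision and error conditional on the observed imbalance. The change should be made, but its absence would not invalidate the trial.

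**What to change.** Replace the selection rule for baseline outcome scores with:

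*Each outcome model includes the T0 value of that outcome, with its interaction with visit, as a fixed covariate for all participants (or T0 as a response with baseline means constrained equal across arms), whatever the baseline comparison shows.*

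Report the baseline table descriptively and do not use baseline tests to choose covariates. The same sentence settles whether T0 is subtracted, modelled or absent.

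The cost is one or two SAP sentences, written before outcomes are compared by arm, and about one parameter per visit. T0 is already measured for every outcome, so no new data or participants are needed.
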